13.0 Study Timelines*

13.1 Describe the anticipated duration needed to enroll all study subjects.

Response:

6 months (from screening to recruitment into the study)

13.2 Describe the duration of an individual subject's participation in the study. Include length of study visits, and overall study follow-up time.

Response:

The study will last during a specific portion of the patient's treatment; it will finish before the patient's treatment has been completed. They will have followed up visits to finish their orthodontic treatment. The full duration of the study is expected to be 5 months +/- 1 month depending on patient compliance. Initial records will be collected at T0. Upon removal of the device, T1 will records will be taken (lateral cephalometric radiograph and digital scan; final records for this study).

13.3 Describe the estimated duration for the investigators to complete this study (i.e. all data is collected and all analyses have been completed).

Response:

18 months

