1.0 Study Summary

Study Title	A Comparison of Class II correction using the Carriere Motion Appliance versus an In-Office Sectional Appliance: Treatment Effects and Efficiency
Study Design	Pilot randomized clinical trial
Primary Objective	1. To evaluate total treatment time, in months, from the initial bonding appointment until a Class I molar relationship has been achieved and the appliance has been removed (T1) using either the Carriere Motion Appliance (CMA) or an in-office fabricated sectional appliance
Secondary Objective(s)	To evaluate secondary tooth movements (mm, degrees) and changes in skeletal measurements after Class II molar correction using the either the CMA or an in-office sectional appliance, by comparing lateral cephalometric radiograph measurements and digital study model measurements taken at the Initial Records appointment prior to treatment(T0) and immediately after removal of appliance – when a Class I molar relationship has been achieved (T1)
Research	Class II Correction Appliances: CMA vs. a sectional, in

Page 4 of 49

Intervention(s)/	office fabricated appliance
Investigational	
Agent(s)	
IND/IDE #	N/A
Study Population	12-17Y11M male and female patients
Sample Size	16 per treatment group (N = 32)
Study Duration for	5 months +/- 1 month
individual	
participants	
Study Specific	CMA= Carriere Motion Appliance
Abbreviations/	ss = Stainless-steel
Definitions	Sagittal first approach = correcting the antero-posterior occlusal relationship prior to the leveling and aligning phase of orthodontic treatment Class I molar relationship = The position of the mesiobuccal cusp of the maxillary first permanent molar occludes distally to the buccal groove of the mandibular first molar, and its distal buccal cusp is positioned in the embrasure between the mandibular first and second molars, when in centric occlusion Class II molar relationship = An occlusal relationship where the buccal groove of the mandibular first molar is positioned distal to the mesiobuccal cusp of the maxillary first molar, when in centric occlusion LFH = lower facial height

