There are a limited number of studies reporting treatment duration of Class II correction phase using the CMA. The appliance is more efficient for growing patients, but it is also effective for adults. ¹⁰ The CMA workbook states that Class II correction for adults takes an average of 5 months to complete, while children should achieve Class II correction in an average of 3 months. ¹⁰ All studies reporting duration of Class II correction were performed on adolescent patients or growing patients. One study reported 4.9 months for patients with skeletal Class I and 4.2 months for patients with skeletal Class II, with a combined average of 4.6 months.

¹⁶ Another study reported an average of 4.28 months, a third reported 4.4 months, and a fourth study reported an average of 5.2 months. ^{12,14,15} A fourth study reported 6.3 months for total Class II correction time when using a CMA. ¹³ When measuring combined total treatment time (CMA followed by fixed appliances) one study reported an average combined total treatment time be 32.3 months with a conclusion that the CMA is not an efficient way to treat Class II malocclusions. ¹³ However, a second study reported a total treatment time of 18.2 months (5.2 months for CMA and 13.0 months for the rest of the treatment duration), and a third reported an average combined treatment time of 17.6 months. ^{12,15}

One study measured long-term effects of patients treated with a CMA followed by functional fixed appliance. Results indicated minor changes in molar movement when comparing CBCT measurements taken after removal of the fixed appliance and at a 4-year follow up. However, the inclusion criteria for this study were subjects with a Class I skeletal relationship, and an Angle Class II relationship of at least ½ cusp. The significant changes measured were mesial crown tipping of the maxillary first molars and lingual crown torquing of the mandibular incisors.¹⁸

CMA From the Patient's Perspective

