7.0 Local Number of Subjects

7.1 Indicate the total number of subjects that will be enrolled or records that will be reviewed locally.

Response: 16 subjects per treatment group, (N = 32)

Page 15 of 49

7.2 If applicable, indicate how many subjects you expect to screen to reach your target sample (i.e. your screen failure rate).

Response:

Approximately 720 to 840 subjects

7.3 Justify the feasibility of recruiting the proposed number of eligible subjects within the anticipated recruitment period. For example, how many potential subjects do you have access to? What percentage of those potential subjects do you need to recruit?

Response:

Our study will be screening the entire prospective patient pool in the University at Buffalo School of Dental Medicine's orthodontic clinic for the first- and second-year residents. One operator (AN) will instruct all residents completing patient screenings and acceptance of patients on criteria necessary to become a subject in the current study. The same operator will also evaluate all eligible subjects and see if they meet all inclusion criteria and proceed to inform the subjects of their eligibility and purpose of the study. Each resident can screen approximately 60-70 patients over 6 months. If we utilize the patient pools of twelve residents, we can approximate 720 to 840 patients total. Not all patients will meet the inclusion criteria required for the study, and other treatment modalities of Class II correction are available as a part of comprehensive orthodontic treatment. Therefore, not all Class II patients who meet the criteria will be using the CMA or in-office appliance for Class II correction as a part of their comprehensive orthodontic treatment.

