Isolation will then be removed and the patient will be instructed to wear the essix retainer 24 hours a day and to only take it out to eat and when completing hygiene methods. The patient will be given Force 1 Class II elastics (1/4, 6 oz) and will be instructed on how to place them from either the hook on the canine pad (CMA group) or the hook on the canine bracket (in-office appliance group) to the button on the mandibular first molars. The patient will be instructed to wear the elastics 24 hours a day and to only remove them when eating and completing hygiene methods, and to change elastics daily.

The patient will be seen 1 month later and will be given Force 2 Class II elastics (3/16, 8 oz) and will be instructed to wear them using the same protocol for the remainder of their class II correction. The patient will be evaluated each month until a Class I molar and canine relationship has been obtained.

Once a Class I molar and canine relationship has been obtained, The CMA or in office appliance will be removed, and an intraoral scan and lateral cephalometric radiograph will be taken immediately after removal of the appliance(s) (T1). The

total duration (in months) of Class II correction, starting at the bonding appointment and ending at the T1 appointment will be recorded for each subject.

Superimposition & Data Analysis

Once T0 and T1 records are obtained, lateral cephalometric tracing and measurements will be completed and recorded by one operator (AN). Superimpositions will be constructed using T0 and T1 lateral cephalometric tracings. Initial cephalometric measurement (T0) will be subtracted from final cephalometric measurements (T1) for each value (Please see table in section 12.2 for a complete list of lateral cephalometric measurements and their descriptions).

Intraoral scan data will be collected with an iTero Element 3D Scanner. Digital models will be superimposed using the Best fit method described in a study conducted by Grünheid and Larson. Maxillary model superimpositions will be used to address the difference in maxillary first molar and canine rotational positions before versus after Class II correction (°). Mean values for all measurements (lateral cephalometric and digital model superimposition) will be calculated for each treatment group and statistical analyses will be ran using he Statistical Package for the Social Sciences (SPSS) to compare means.

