19.0 Data Management and Analysis*

19.1 Describe the data analysis plan, including any statistical procedures. This section applies to both quantitative and qualitative analysis.

Response:

Intra-examiner reliability will be addressed by randomly selecting 5 lateral cephalograms 2 weeks after initial measurements were performed and having the same operator (AN) repeat the landmarking, superimpositions and measurements. The same operator will also repeat measurements on 5 casts 2 weeks after measurements are conducted for the maxillary first molar and canine rotational measurements. Intra-class correlation coefficients will be calculated in order to determine intra-examiner reliability based on the first and second measurements (P < 0.05).

Statistical analysis will be performed using SPSS. A Shapiro-Wilk test will be run to assess for normality. If the data are normally distributed, independent ttests will be ran to compare means between the two treatment groups. If normality assumptions are not met, a Wilcoxon Rank-Sum test will be used to compare means between the two treatment groups for all measurements.

19.2 If applicable, provide a power analysis.

NOTE: This may not apply to certain types of studies, including chart/records reviews, survey studies, or observational studies. This question is asked to elicit whether the investigator has an adequate sample size to achieve the study objectives and justify a conclusion.

Response:

Sample size estimation: Based on a power of 80% and a significance level of 0.05, it was determined that a sample of size of 16 per treatment group, or a total of 32 participants, would be sufficient in order to have a standardized effect size of 1.02366. These calculations were made based on mean values reported for total treatment time (in months) to achieve Class II correction using a CMA in previous studies. ^{12,14,15,16}

19.3 Describe any procedures that will be used for quality control of collected data.

Response:

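### Subjects who never reach Class I, or who are withdrawn, have no place in the primary time-to-correction comparison, and 16 per group leaves no reserve for losing them

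*Protocol*

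**What the plan says.** Section 5.1 defines T1 as the visit at which the appliance comes off because molar correction has been achieved. Section 12.2 lists the primary variable as months from bonding to T1. Section 12.1 gives the follow-up rule: "The patient will be evaluated each month until a Class I molar and canine relationship has been obtained". The appliance is then removed and the T1 scan and cephalogram are taken. No maximum follow-up is stated.

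On expected length, section 13.2 says "The full duration of the study is expected to be 5 months +/- 1 month depending on patient compliance", and the summary in section 1.0 gives "5 months +/- 1 month" without the word expected. Section 13 allows 6 months for enrolment and 18 months for the whole study, analysis included.

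Section 19.1 compares the arms by independent t-test or, if normality fails, by Wilcoxon rank-sum test. Section 22.1 lists irregular attendance, root resorption and periodontal problems among the grounds for withdrawal. Section 22.3 says the data of withdrawn subjects are not used because they are incomplete. Section 22.2 says such data are destroyed, while 22.3 says they are held for about three years. On either reading they are not analysed.

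The sample size in section 19.2 is "Based on a power of 80% and a significance level of 0.05", for a "standardized effect size of 1.02366". It concludes that "a sample of size of 16 per treatment group, or a total of 32 participants, would be sufficient". Section 7.1 enrols that same number.

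**The concern.** In a time-to-event question, the subjects without an event carry information: they took at least as long as they were observed. This protocol removes them in two ways. A subject who never reaches Class I has no T1, hence no duration, and no rule says how to record that person. A withdrawn subject is excluded outright. Neither loss is likely to be random. Section 13.2 itself ties duration to compliance, and poor attendance is a ground for withdrawal. Root resorption and periodontal problems plausibly become more likely the longer an appliance is in place.

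The primary comparison is then between arms of successful completers rather than between arms as randomised. If the slower appliance loses more of its slow subjects, the difference is pulled towards zero. If the faster one does, the difference is exaggerated. The same subjects also leave the skeletal and dental comparisons (hypotheses 2 and 3).

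**Working it through.** **1. Reproduce the sample size.** Inputs from section 19.2: d = 1.02366, alpha = 0.05, power 80%, n = 16 per group. For a two-sided two-sample t-test the noncentrality is d × √(n/2) = 1.02366 × √8 = 2.895 on 30 df, and the power is 80.0%. Solving for n gives 16.0001. Solving for d at n = 16 gives 1.02366. A one-sided test would need 13, so two-sided is the version used. The figure is reproduced exactly, with no allowance for loss.

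**2. Who has a duration under the text as written?**
- Corrects at month 8, say: still seen monthly, so has a duration, a scan and a film.
- Never corrects, or is uncorrected when data collection closes: none of these, and no rule.
- Withdrawn: excluded under 22.3.

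**3. How many would be lost through slowness alone?** Enrolment takes 6 of the 18 months, leaving 18 − 6 = 12 months after the last enrolment, less analysis time. The documents give no SD, so assume normal durations and take SD = 2.0 months as a wide case. The share beyond c months is 1 − Φ((c − mean)/SD).
- Mean 6.3 (the longest cited in section 4.1), c = 12: 1 − Φ(2.85) = 0.2%.
- Mean 6.3, c = 10 (two months kept for bonding delay and analysis, assumed): 1 − Φ(1.85) = 3.2%, or 16 × 0.032 = 0.5 subject per arm.
- Mean 5.2, c = 10: 1 − Φ(2.40) = 0.8%.

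Slowness alone therefore loses few. The open quantity is how many never correct or are withdrawn, and the documents give no rate.

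**4. Cost of losing a few at random.** Power at d = 1.02366 by evaluable subjects per group:

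| Per group | Power |
|---|---|
| 16 | 80.0% |
| 15 | 77.2% |
| 14 | 74.1% |
| 13 | 70.7% |
| 12 | 66.9% |

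**5. Cost if the losses are the slow subjects.** As a bounding case, remove only the k slowest of 16 in the slower arm. For 16 normal values the three largest have expected positions 1.766, 1.285 and 0.990 SD above the mean. The mean of those remaining falls by (sum of the k largest)/(16 − k). Power is by simulation under the same normal model.

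| k | Fall in mean (SD) | Difference left (SD) | Power |
|---|---|---|---|
| 1 | 1.766/15 = 0.118 | 0.91 | 72% |
| 2 | 3.051/14 = 0.218 | 0.81 | 62% |
| 3 | 4.041/13 = 0.311 | 0.71 | 52% |

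Losing two slow subjects from one arm costs more than losing two at random from each arm (74.1%), because the estimate is biased as well as less precise.

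**The case against.** A reader might infer something stronger: that participation is fixed at 4 to 6 months, so anyone slower falls out by schedule. Section 4.1 seems to invite this, since "A fourth study reported 6.3 months for total Class II correction time when using a CMA". The documents do not support it. Section 13.2 states an expectation that depends on compliance. The summary omits that word but gives no stopping rule. Section 12.1 follows each subject until Class I. Any calculation that truncates durations at six months has no basis in the protocol. The 6.3-month study is also not among the four used for the sample size.

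A second objection is that the handling of incomplete durations often belongs in a statistical analysis plan, which is not at hand. That is fair for the fine detail. However, the T1 definition, the exclusion of withdrawn subjects' data and the named tests are all in the protocol, so a later plan would have to depart from it.

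A third is that almost everyone may finish, in which case the choice of method hardly matters. That may prove true and it limits the severity. It does not remove the gap, because the loss is related to the outcome and the sample has no slack.

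**Conclusion.** The point holds as a moderate defect in the primary comparison. Duration exists only for successes, withdrawn subjects are discarded, and the tests named need a finished value for everyone. Subjects who do not correct or who leave early are therefore excluded for reasons linked to the outcome.

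The expected number is probably small and cannot be derived from the documents. With 16 per group, one to three selectively lost subjects in one arm would bring power to roughly 72% to 52% and bias the difference by about 0.1 to 0.3 SD. Those figures assume normal durations and the least favourable pattern of loss, so they are a bound and not a forecast. The reproduction of the sample size rests on no assumption beyond a two-sided t-test.

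**What to change.** - Set one common data cut-off counted from bonding, identical in both arms and under 12 months so that it fits the 6-month enrolment within 18 months. This is a data rule only; treatment continues as the clinic decides.
- Include every randomised and bonded subject in the primary comparison. Record those uncorrected at the cut-off as not reached. Where consent allows, keep withdrawn subjects up to their last visit, and reconcile sections 22.2 and 22.3 accordingly.
- Compare durations with a log-rank test, or with the rank-sum test already named, ranking subjects uncorrected at the cut-off last. Censoring at the common cut-off is harmless. Censoring at withdrawal may still be informative, so report the reasons by arm.
- Report the number not corrected per arm, and state that the T0 to T1 skeletal and dental comparisons apply to corrected subjects only.
- Make clear in section 1.0 that the 5-month figure is an expectation, as in 13.2.

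The cost is some protocol wording and slightly more analysis work. A log-rank or rank result is also not a simple difference in mean months, so hypothesis 1 would need matching wording. Enrolling more subjects would restore power against random loss (18, 19 or 20 per group for assumed losses of 10%, 15% or 20%), but would not remove the bias.

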14.0 Setting

14.1 Describe all facilities/sites where you will be conducting research procedures. Include a description of the security and privacy of the facilities (e.g. locked facility, limited access, privacy barriers). Facility, department, and type of room are relevant. Do not abbreviate facility names.

NOTE: Examples of acceptable response may be: "A classroom setting in the Department of Psychology equipped with a computer with relevant survey administration software," "The angiogram suite at Buffalo General Medical Center, a fully accredited tertiary care institution within New York State with badge access," or, "Community Center meeting hall."

Response:

The study will be conducted in the Orthodontic Clinic at the University at Buffalo School of Dental Medicine. The facility has 20 individual operatories for orthodontic residents to administer treatment. Each operatory is equipped with all standard of care equipment and necessary instruments to treat patients in full orthodontic capacity. The entire facility and all of the computer systems are equipped with encrypted login devices connected to each operatory computer. Each computer can be accessed by university issued identification badges, once activated each individual is instructed to input their credentials in order to access

the university's patient management software, AXIUM. University at Buffalo School of Dental Medicine Orthodontic clinic patients can only be viewed by SDM faculty, staff and residents/SDM students, all others are restricted from accessing. Patient electronic health records along with schedules are not left open while treating patients to avoid any neighboring patients view of other's personal information. The computers will automatically log out of the individual's username after thirty minutes of idle time. Any input to the patient's electronic health record, notes, diagnostic codes, treatment plans, etc., are required to be reviewed by the supervising faculty for completeness and approved through the faculty's identification card swipe prior to dismissal of the patient. The facility is restricted to faculty, staff and residents of the University at Buffalo School of Dental Medicine's Orthodontic Clinic. No other individuals have access to the facility, and patients are only allowed to enter accompanied by resident or faculty during appropriate clinic operating hours and supervision. The facility is otherwise locked outside of clinic hours and restricted only to the custodian staff overnight and on the weekends. The intraoral 3D scanner located in the university's Orthodontics clinic has its own operatory in a designated corner of the facility, with appropriate barriers and positioning of the iTero scanner to prevent disclosure of private sensitive information to those around. There is a designated computer laboratory for residents and faculty to work on research projects, data analysis, treatment planning, and for educational purposes. There is a limit to the number of occupants in the computer room at any given time, and there is adequate spacing between individual computers to ensure individual privacy. The same security measures are present for the computers in the laboratory as in the operatories.

14.2 For research conducted outside of UB and its affiliates, describe:

- Site-specific regulations or customs affecting the research
- Local scientific and ethical review structure

NOTE: This question is referring to UB affiliated research taking place outside UB, i.e. research conducted in the community, school-based research, international research, etc. It is not referring to multi-site research. UB affiliated institutions include Kaleida Health, ECMC, and Roswell Park Cancer Institute.

Response:

N/A: This study is not conducted outside of UB or its affiliates.

■ N/A: This study is not conducted outside of UB or its affiliates.

15.0 Community-Based Participatory Research

15.1 Describe involvement of the community in the design and conduct of the research.

NOTE: Community-Based Participatory Research (CBPR) is a collaborative approach to research that equitably involves all partners in the research process and recognizes the unique strengths that each brings. CBPR begins with a research topic of importance to the community, has the aim of combining

knowledge with action and achieving social change to improve health outcomes and eliminate health disparities.

Response:

- N/A: This study does not utilize CBPR.
- 15.2 Describe the composition and involvement of a community advisory board.

Response:

N/A: This study does not have a community advisory board.

